10 SUPPORTING DOCUMENTATION AND OPERATIONAL CONSIDERATIONS

10.1 Regulatory, Ethical, and Study Oversight Considerations

10.1.1 Informed Consent Process

10.1.1.1 Consent/Accent and Other Informational Documents Provided To Participants

Consent forms describing in detail the device intervention, study procedures, and risks are given to the participant and written documentation of informed consent is required prior to device intervention. The following consent materials are submitted with this protocol:

- Informed Consent Form

10.1.1.2 Consent Procedures and Documentation

Prior to engagement with the patient, the physician will determine patient eligibility for the study. Procedures for diagnosis will not fall under the scope of the study itself and the participating entities of the study are not responsible for costs associated with said procedures.

Informed consent is a process that is initiated prior to the individual's agreeing to participate in the study and continues throughout the individual's study participation. Potential participants will be provided information about the research project that is understandable and that permits them to make an informed and voluntary decision about whether or not to participate. Consent forms will be Institutional Review Board (IRB)-approved and the participant will be asked to read and review the document. The patient will be asked to provide verbal assent. Amongst the information provided will be potential risks. A verbal explanation will be provided in terms suited to the participant's comprehension of the purposes, procedures, and potential risks of the study and of their rights as research participants. This will include an overview of the device and its functionality along with the intended uses of the device. During this stage, the physician will also inform the patient that no diagnosis will be made from use of the device and that their contribution will be used to help determine the validity and capabilities of the device. The patient will have the opportunity to carefully review the written consent form and ask questions prior to signing. The participants should have the opportunity to discuss the study with their family or surrogates or think about it prior to providing verbal assent. The patient will sign the informed consent document prior to any procedures being done specifically for the study. Participants will be informed that participation is voluntary and that they may withdraw from the study at any time, without prejudice. A copy of the informed consent document will be given to the participants for their records. The informed consent process will be conducted and documented in the source document (including the date), and the form signed, before the participant undergoes any study-specific procedures. The rights and welfare of the participants will be

protected by emphasizing to them that the quality of their medical care will not be adversely affected if they decline to participate in this study. We have no proposed waivers or alternatives to informed consent apart from the patient's decision not to participate. We also do not anticipate special circumstances while obtaining consent. Due to resource constraints, speakers of a language other than English will not be allowed to participate in this study.

Note that all procedures conducted at the Hospital of the University of Pennsylvania and Penn Presbyterian Medical Center will be beholden to the Penn IRB.

10.1.2 Study Discontinuation and Closure

This study may be temporarily suspended or prematurely terminated by the principal investigator (PI) if there is sufficient reasonable cause. Written notification, documenting the reason for study suspension or termination, will be provided by the suspending or terminating party to study participants and the investigator. If the study is prematurely terminated or suspended, the PI will promptly inform the Institutional Review Board (IRB) and provide the reason(s) for the termination or suspension.

Circumstances that may warrant termination or suspension include, but are not limited to:

- Determination of unexpected, significant, or unacceptable risk to participants
- Demonstration of efficacy that would warrant stopping via ongoing statistical analysis
- Insufficient compliance to protocol requirements
- Data that are not sufficiently complete and/or evaluable
- Determination of futility

Study may resume once concerns about safety, protocol compliance, and data quality are addressed, and satisfy the IRB. In terminating the study, the PI will ensure that adequate consideration is given to the protection of the subjects' interests.

10.1.3 Confidentiality and Privacy

Participant confidentiality and privacy is strictly held in trust by the PI and the study team. This confidentiality is extended to cover the clinical information relating to participants. Therefore, the study protocol, documentation, data, and all other information generated will be held in strict confidence. No information concerning the study or the data will be released to any unauthorized third party without prior written approval of the PI.

Recorded data will include the following: study participant alphanumeric key, mobile app profile anonymization ID (if applicable), incentive spirometer device identification key, exercise metrics, exercise settings, exercise dates and time stamps, SPO2 measurements, pulmonary function lab spirometry results, pain scores, survey responses, age, weight, height, and sex at birth. Age, weight, height, and sex at birth are necessary identifiers because they determine target incentive spirometry volumes for an individual.

Participant research data will be kept on PennBox and a private secure cloud-based database only accessible to members of the research team. Information regarding patient names and the dates of study participation will be collected on consent forms, which will be stored under lock and key in paper format in the investigator's office and uploaded to their patient record.

All research activities will be conducted in as private a setting as possible.

The authorized representatives of the sponsor and representatives of the Institutional Review Board (IRB) may inspect all documents and records required to be maintained by the investigator. The clinical study site will permit access to such records.

The following list provides information on the data being stored. Please note that the “final data set” constitutes any data that will be used in subsequent analysis and may be published at the discretion of study team members or the PI.

- Patient Information – collected for the purposes of evaluating eligibility
 - Identification of scheduled lung resection surgery - used in final data set
 - Randomized Alphanumeric Key to Label Patient Data - used in final data set
 - Age , weight, height, sex at birth- used in final data set
 - Birthdate - NOT used in final data set
 - Medical record number - NOT used in final data set
 - Name - NOT used in final data set
- Timestamped inspiratory breath data (inspiratory volume over time, inspiratory air flow rate over time) – will be used in the “final data set”
- Blood oxygen saturation - will be used in the “final data set”
- Pain scores - will be used in the “final data set”
- Digital incentive spirometer device identification key – will be used in the “final data set”
- Pulmonary function lab spirometry results – will be used in the “final data set”
- Discharge survey responses – will be used in the “final data set”

Separately, our consent forms (which are stored on Presbyterian Medical Center servers and are not transferred to any other location or computer):

- Patient Name
- Date of Study Participation
- Randomized Alphanumeric Key to Label Patient Data
- Digital incentive spirometer device identification key

At the end of the study, all records will continue to be kept in a secure location for as long a period as dictated by the reviewing IRB and Institutional policies. All other data/information will not be stored beyond the scope of the patient's engagement with the study.

Patient data (timestamped inspiratory breath data, blood oxygen saturation data, pulmonary function lab spirometry results, age, weight, height, sex at birth, and pain scores) will be tagged with a randomized alphanumeric combination that will distinguish the data from one another amongst study participants. Patient names, medical record numbers, and birthdates will only be used in the initial screening process and study intervention administration, and they will not appear on data used for analysis and results. The only set of data maintained with patient names, medical record numbers, and birthdates will be internally stored on Presbyterian Medical Center servers and on consent forms.

Study participant research data will be shared via the private secure cloud-based database accessible only to study members or PennBox for study analysis. Inspiratory breath data collected with the digital IS systems will be uploaded directly to the secure cloud-based database via the HUP or PPMC WiFi. Blood oxygen saturation data, pulmonary function lab spirometry results, age, weight, height, sex at birth, and pain scores will be stored on Presbyterian Medical Center computers and will not be transferred electronically (e.g., via email) to any other computer, except to study members via PennBox. A certificate of confidentiality will not be required for this study.

10.1.4 Future Use of Stored Specimens and Data

Data collected for this study will be transferred via a private secure cloud-based database and PennBox. Scanned consent forms will be stored solely on Penn Medicine computers and will not be transferred to any other computer. After the study is completed, archived data will be stored on a password-protected, encrypted computer.

No biological samples will be drawn or collected from participants during this study.

During the conduct of the study, an individual participant can choose to withdraw consent to have biological data (i.e., diagnoses or measurements) stored for future research. At this point, the study team will access the consent forms on PPMC servers and use the linking set to determine which data needs to be eliminated from all records.

10.1.5 Safety Oversight

Internal reviews of data security by the PI will be completed to ensure human subjects' protection and data integrity. The PI will comprise the Safety Assessment Committee (SAC) and verify items such as proper data transferral to the cloud-based database, proper user interfacing with the database, etc.

10.1.6 Clinical Monitoring

Clinical site monitoring is conducted to ensure that the rights and well-being of trial participants are protected, that the reported trial data are accurate, complete, and verifiable, and that the conduct of the trial adheres as best as possible to the currently approved protocol/amendment(s), with International Conference on Harmonisation Good Clinical Practice (ICH GCP), and with applicable regulatory requirement(s).

- The principal investigator will be conducting the monitoring of data collection. Monitoring will be done on-site at least once during the course of the study and at the conclusion of the study. In addition, the monitoring will be comprehensive. Steps will be taken to ensure that the rights and well-being of trial participants are protected, that the reported trial data are accurate, complete, and verifiable, and that the conduct of the trial adheres as best as possible to the currently approved protocol/amendment(s), with ICH GCP, and with applicable regulatory requirement(s). Monitoring reports will be distributed to the clinical team and Sponsor within 2 weeks of that review.
- Clinical site monitoring will be conducted by the PI at least once during the course of the study to ensure that all protocols are being followed regarding patient safety and device usage. This portion of the monitoring will not be formalized in the form of a report unless any concerns arise during the review. In this case, the monitoring report will be sent to the study team within 1 week of that review.

10.1.7 Quality Assurance and Quality Control

All monitoring and audits are to be performed while adhering, as best as possible, to International Conference on Harmonisation Good Clinical Practice (ICH GCP) E6(R2).

The PI will perform internal quality management of study conduct, data collection, documentation and completion.

Quality control (QC) procedures will be implemented beginning with the data entry system and data QC checks that will be run on the database will be generated. Any missing data or data anomalies will be communicated to the site for clarification/resolution.

The data quality management monitoring will be conducted by the PI. They will be responsible for both Quality Control (QC) and Quality Assurance (QA).

The monitors will verify that the clinical trial is conducted and data are generated, documented (recorded), and reported in compliance with the protocol.

The investigational site will provide direct access to all trial related sites, source data/documents, and inspection by local and regulatory authorities.

10.1.8 Data Handling and Record Keeping

10.1.8.1 Data Collection and Management Responsibilities

Data collection is the responsibility of the study team under the supervision of the principal investigator. The investigator is responsible for ensuring the accuracy, completeness, legibility, and timeliness of the data reported.

All source documents should be completed in a neat, legible manner to ensure accurate interpretation of data and follow ALCOAC standards (attributable, legible, contemporaneous, original, accurate, and complete). If any responses are illegible, the PI or member of the study team must ask the patient to clarify that response verbally. Inspiratory breath data will be recorded by the digital IS devices and transferred via HUP or PPMC's WiFi network to a secure cloud-based database for research use. Patient blood saturation, pulse oximetry, age, weight, height, sex at birth, and pulmonary function lab spirometry results will be recorded on a computer linked and managed by the Hospital of the University of Pennsylvania and Penn Presbyterian Medical Center, and then data will be obtained from EPIC and transferred via the cloud-based database or PennBox for research use. This computer will be located on the floor where all patients enrolled in the study will be managed post-operatively.

Hardcopies of the consent forms will be scanned, stored and maintained at Penn Presbyterian Medical Center in room 245B. Data recorded in the data collection software derived from source documents should be consistent with the data recorded on the source documents. Patient participation in the study will not be recorded in the EMR.

Regarding data processing, any and all listed study members may be involved in data processing (i.e., statistical analysis) as data will not contain patient names at this point in the analysis.

10.1.8.2 Study Records Retention

Study documents (namely consent forms) should be retained for a minimum of 2 years after the last approval of a marketing application in an International Conference on Harmonization (ICH) region and until there are no pending or contemplated marketing applications in an ICH region or until at least 2 years have elapsed since the formal discontinuation of clinical development of the study. These documents should be retained for a longer period, however, if required by local regulations. No records will be destroyed without the written consent of the PI.

10.1.9 Protocol Deviations

Protocol deviations will be continuously monitored through ongoing verification of patient information to ensure they fit eligibility criteria. In the event that protocol deviations are needed to broaden eligibility criteria, the principal investigator must approve of such a change in order to allow the study to fully enroll. The principal investigator must subsequently report this change to the IRB. Any protocol deviations made by the clinical team must be immediately reviewed and relayed to the principal investigator. These scenarios should be reported to the Sponsor within 10

business days of discovery. Reporting to IRB should follow local requirements. The PI and the study team should document all scenarios where the protocol is not followed and provide, in particular:

- Who deviated from the protocol
- What was the deviation
- When did the deviation occur
- How did the deviation happen
- What is the impact of the deviation
- A root cause analysis of why the deviation occurred

If the assessment is determined to be of limited impact (minor deviation), the documentation for this assessment and the outcome should be reported to the Sponsor at the time of annual report. Reporting to the IRB should follow specific local requirements.

If the assessment results in a determination that any of the following are potentially affected, the deviation would be considered of significant impact:

- adversely affects the integrity of the data; OR
- violates the rights and welfare of participants, OR
- affects the subject's willingness to participate in research.
- there is a potential for an overall impact on the research that should be shared with the IRB for consideration and development of next best steps to address it

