4 STUDY PLAN

4.1 Study Design

We hypothesize that use of the investigational device will have a positive impact on patient incentive spirometry adherence. This is a single-arm, exploratory study that will be conducted at the Hospital of the University of Pennsylvania (HUP) and Penn Presbyterian Medical Center (PPMC). The digital IS utilizes a sensor to measure inspiratory breath volume and flow rates, and this data, as well as the time stamps, are transmitted wirelessly to a secure cloud database and a companion mobile-based app. The IS and app incorporate features to instruct and remind patients about their exercises, which include auditory and visual cues as well as a gentle auditory and haptic reminder to perform exercises. Furthermore, the app has additional features to encourage breathing exercises in the form of gamification strategies, and separate interfaces for patients and medical staff to monitor device usage. All of the features are aimed at improving patients' adherence to incentive spirometry.

Subjects will be recruited from patients undergoing any lung resection surgery performed by [name], [name], and/or [name] at HUP and/or PPMC and for which an incentive spirometer is expected to be used by the patient after their surgery. The target enrollment for the study is 30 subjects. The duration of the subject's participation with the trial will be for their entire postoperative hospital stay up to 1 week postoperatively. At the beginning of the subject's participation, study activities will be focused on informed consent, instruction on use of the digital IS, and obtaining baseline inspiratory volume measurements. Most of the remainder of the subject's participation time will be focused on passive data collection performed by the digital IS.

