9.3 Populations for Analyses

The population will include adult patients.

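### Section 10.1.9 lets the principal investigator broaden eligibility by protocol deviation to fill enrolment, without requiring an amendment or prior IRB approval, and the planned output would not separate the patients so admitted

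*Combined protocol and SAP*

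**What the plan says.** Section 10.1.9 (Protocol Deviations) opens with a check on eligibility: "Protocol deviations will be continuously monitored through ongoing verification of patient information to ensure they fit eligibility criteria". The next sentence lets the criteria themselves move. It begins "In the event that protocol deviations are needed to broaden eligibility criteria" and continues "the principal investigator must approve of such a change in order to allow the study to fully enroll". Then: "The principal investigator must subsequently report this change to the IRB". Later the section adds "Reporting to IRB should follow local requirements", and it requires every departure from the protocol to be documented (who, what, when, how, impact, root cause).

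The analysis sections set no boundary of their own. Section 9.3 reads, in full, "The population will include adult patients". Section 9.4.2 gives the primary result as an average and standard deviation over all patients, with no comparator. Sections 9.4.5 (baseline descriptive statistics) and 9.4.7 (subgroup analyses) are marked as not applicable. Section 4.1 states "The target enrollment for the study is 30 subjects", and section 9.2 bases that number on expected caseload over 3 months.

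**The concern.** A prospective change to entry criteria is an amendment. Section 10.1.9 treats it as a deviation, gives the decision to one person, states completion of enrolment as the reason, sets no limit on the widening, and places the IRB after the decision. The other oversight roles do not supply a second check: section 1.2 lists no separate sponsor, and sections 10.1.5 to 10.1.7 give safety oversight, monitoring, quality control and quality assurance to the principal investigator.

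Two things are at stake. One is independent review before new kinds of patient are approached. The other is what the result means. A single-arm mean describes only the patients who produced it. If the criteria widen part-way, the mean becomes a mixture whose proportions depend on accrual, and nothing in the planned tables would show that.

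**Working it through.** **Reading the text.**

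1. Mechanism (10.1.9): deviation; no amendment is mentioned.
2. Approver and reason (10.1.9): the principal investigator, to complete enrolment.
3. IRB (10.1.9): informed after the investigator's approval. The sentence on local requirements concerns reporting, not prior approval.
4. Analysis set (9.3): adults, with no link to sections 5.1 and 5.2.
5. Output (9.4.2, 9.4.5, 9.4.7): one pooled mean and SD per primary endpoint, no baseline table, no subgroups.

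Items 1 to 3 mean that the text does not prevent entry under criteria the IRB has not approved. Items 4 and 5 mean that such patients would not be distinguished in the planned output.

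**Size.** There is no figure in the plan to reproduce. The 30 is a feasibility count, and section 9.1 states no hypothesis, so no alpha or power is affected. What follows is an illustration on assumed inputs; the documents give neither the number of such patients nor how they would differ.

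Let k of 30 patients enter under wider criteria, with a mean differing by d SD from the rest. The shift in the pooled mean is (k/30) × d SD. As a yardstick (the plan computes no interval), the 95% half-width at n = 30 is t(0.975, 29)/√30 = 2.045/5.477 = 0.373 SD.

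| k (assumed) | k/30 | Shift, d = 0.5 | Shift, d = 1 |
|---|---|---|---|
| 3 | 0.10 | 0.05 SD | 0.10 SD |
| 6 | 0.20 | 0.10 SD | 0.20 SD |
| 10 | 0.33 | 0.17 SD | 0.33 SD |

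The smallest shift is 0.05/0.373 = 13% of the half-width and the largest is 0.333/0.373 = 89%. In that largest case the pooled SD also rises, to √(1 + (1/3)(2/3)(1²)) = 1.106 SD, so the interval would itself widen to about 1.106 × 0.373 = 0.41 SD.

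**What reaching 30 buys.** Suppose enrolment under the existing criteria stopped at 25 (assumed). The half-width would be t(0.975, 24)/√25 = 2.064/5 = 0.41 SD instead of 0.37 SD. The precision gained by widening the criteria to fill the last five places is small.

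**The case against.** The strongest reply is that this is loose wording in a minimal-risk, exploratory study and that other text contains the damage. Several parts of that reply stand.

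- **IRB timing.** A reader might infer that patients will be enrolled before the IRB acts, or that ethical review is removed. The text does not say so. The word in 10.1.9 orders the investigator's approval and the report; it is silent on when patients enter. Section 10.1.1.2 places all procedures at both hospitals under the Penn IRB, and 10.1.9 refers IRB reporting to local requirements. What stands is narrower: prior approval is not expressly required.
- **Contradiction with 10.1.6.** A reader might see a direct conflict, because 10.1.6 speaks of the currently approved protocol and amendments. But that commitment is only to adhere as far as possible, and the mention of amendments suggests that an amendment route was expected. The two sections fit badly; they do not clearly contradict each other.
- **Unsuitable patients.** A reader might infer that people for whom spirometry is inappropriate (exclusion 3) could be admitted. Nothing in 10.1.9 says which criteria would be relaxed, that exclusion rests on the investigator's own opinion, and 7.2 lets the investigator withdraw anyone who meets an exclusion.
- **Traceability.** A reader might conclude that affected patients could never be identified. The deviation records in 10.1.9 would identify them, and 10.1.3 keeps the scheduled surgery, age, weight, height and sex in the final data set. The gap is in the planned output, not in the study records.
- **Magnitude.** All the shifts above are smaller than the 0.37 SD half-width, and only the extreme case comes near it. They show what is possible and are not evidence of distortion.

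None of this supplies the missing requirement for an approved amendment, or a planned way to show the result by entry criteria.

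**Conclusion.** The point holds in limited form. Section 10.1.9 states a faulty rule; this is not merely missing detail. It permits eligibility to be broadened by deviation on the principal investigator's approval, for the sake of enrolment, with no amendment and no prior IRB approval required. Sections 9.3 and 9.4 would then pool those patients without distinction. The harm is to participant oversight and to the interpretation of an uncontrolled mean; no error rate is involved.

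The size is unknown. The range of 0.05 to 0.33 SD rests entirely on assuming 3 to 10 affected patients and a difference of 0.5 to 1 SD, and if the provision is never used there is no effect. This is a cheap improvement, not a threat to the study.

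**What to change.** In 10.1.9, replace the two sentences on broadening eligibility with: *Any change to eligibility is made by protocol amendment approved by the IRB before any patient is enrolled under it; enrolment outside the approved criteria is a reportable deviation.*

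In 9.3, record the protocol version under which each patient was enrolled. Only if the criteria change, report both primary endpoints for patients meeting the original criteria as well as for all patients. For that comparison to have one meaning, the surgical population also needs reconciling: it is any lung resection in 4.1, anatomic resection in 5.1, and robotic anatomic resection in 5.5.

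Cost: a sentence in each section, one extra data field, and a second summary of two endpoints if it is triggered. The real downside is time. Enrolment under new criteria would wait for amendment review, which may matter in a study planned for 3 months; the documents give no review time. Enrolment under the original criteria can continue meanwhile.
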